7.1.2 QTc Stopping Criteria

If a clinically significant finding is identified (including, but not limited to changes from Baseline in QT interval-corrected using Fridericia's formula [QTcF]) after enrollment, the Investigator or qualified designee will determine if the study participant can continue in the study and if any change in participant management is needed. This review of the ECG printed at the time of collection must be documented. Any new clinically relevant finding should be reported as an AE.

A study participant who meets the bulleted criteria based on the average of triplicate ECG readings will discontinue rozanolixizumab and move into the Observation Period. The study participant should be referred to a specialist (ie, cardiologist) and managed as per local guidance.

- QTc >500 msec OR Uncorrected QT >600 msec
- Change from Baseline of QTc >60 msec

For study participants with underlying bundle branch block, follow the discontinuation criteria listed below:

Baseline QTc with Bundle Branch Block	Discontinuation QTc Threshold with Bundle Branch Block
< 450 msec	> 500 msec
450 to 480 msec	≥ 530 msec

See the Schedule of Activities (Section 1.3) for data to be collected at the time of treatment discontinuation and follow-up, and for any further evaluations that need to be completed.

The study participant should follow the visit schedule as described in the protocol and the eCRF be completed accordingly.

7.1.3 Discontinuation due to other adverse events or medical conditions

Study participants **must** permanently discontinue rozanolixizumab **and** move into the Observation Period if any of the following events occur:

1. Study participant develops an illness that would interfere with his/her continued exposure to rozanolixizumab.
2. Study participant has new onset or recurrent neoplastic disease (except for superficial basal or squamous cell carcinoma of the skin not requiring targeted biological therapy, chemotherapy or radiation).
3. Study participant has a serious infective episode requiring hospitalization or iv antibiotic therapy (ie, bacteremia or sepsis, meningitis, osteomyelitis or septic arthritis, pneumonia, or visceral abscess) (see Section 10.25).
4. Study participant has an AE of severe or serious infusion or anaphylactic reaction requiring corticosteroid and/or epinephrine therapy (see Section 10.28) (Sampson et al, 2006).
5. Study participant experiences a serious or recurrent (ie, second occurrence) severe AE of headache, which is considered related to the study medication in the opinion of the investigator.
6. Study participant has a TB test that is confirmed positive or any further evidence suggestive of potential TB infection (eg, exposure) and further examinations result in a diagnosis of active TB or LTBI (Section 8.2.6).
7. Study participant meets potential drug-induced liver injury permanent discontinuation criteria.

If a NTMBI is identified during a study, the same withdrawal procedures as those used for an active TB infection identified during the study should be followed.

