active for MG0007, no further participants will enroll in MG0004 and the study will be closed at the site once all eligible study participants have discontinued MG0004 and had the opportunity to rollover into MG0007.

The maximum duration of the study per study participant will be up to 18 weeks, consisting of a Screening Period (1 to 28 days to account for central laboratory turn-around time), a Treatment Period (6 weeks), and a blinded Observation Period (8 weeks).

1. All study participants who complete the 6-week Treatment Period will roll over into an 8-week Observation Period.
2. All eligible study participants who complete the Observation Period will be invited to be re-randomized into an OLE study to either active dose arm 1 or 2.
3. Study participants who experience disease worsening during the 6-week Treatment Period (eg, an increase of 2 points on the MG-ADL or 3 points on the QMG scale between two consecutive visits) may be considered for rescue therapy (IVIg or PEX) at the discretion of the Investigator.
4. Study participants who need rescue therapy during the 6-week Treatment Period will receive IVIg or PEX and complete any subsequent visit(s). No further infusions of rozanolixizumab will be administered after initiation of rescue therapy. Once the participant completes Visit 10, he or she will move into the 8-week Observation Period.
5. Study participants who complete the Treatment Period and require initiation of rescue therapy after they start the 8-week Observation Period, may either opt to receive IVIg or PEX or complete the EOS visit and immediately roll over into an OLE study where the participant will receive rozanolixizumab. Study participants who opt to receive IVIg or PEX will complete any remaining visits in the Observation Period and will not be invited to join an OLE study.
6. Study participants who did not complete the 6-week Treatment Period because they needed rescue therapy and require initiation of a second course of rescue therapy while in the 8-week Observation Period can roll over to an OLE study if a minimum of 2 weeks have lapsed since completion of the last IVIg or PEX session. The EOS visit must be completed before enrolling into an OLE study. Alternatively, they can be treated with IVIg or PEX. Study participants who opt to receive IVIg or PEX will complete any remaining visits in the Observation Period and will not be invited to join an OLE study .

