7.2 Participant Discontinuation/Withdrawal from the study

Study participants are free to withdraw from the study at any time, without prejudice to their continued care.

A study participant may also be withdrawn at any time at the discretion of the investigator for safety, behavioral, compliance, or administrative reasons.

If the study participant withdraws consent for disclosure of future information, the Sponsor may retain and continue to use any data collected before such a withdrawal of consent.

If a study participant withdraws from the study, he/she may request destruction of any samples taken and not tested, and the investigator must document this in the site study records.

See the Schedule of Activities (Section 1.3) for data to be collected at the time of study discontinuation and follow-up and for any further evaluations that need to be completed.

Study participants **must** be withdrawn from the study if any of the following events occur:

1. Study participant withdraws his or her consent.
2. The sponsor or a regulatory agency requests withdrawal of the study participant.
3. There is confirmation of a pregnancy during the study, as evidenced by a positive pregnancy test.

4. Study participant has active suicidal ideation as indicated by a positive response (Yes) to either Question 4 or Question 5 of the "Since Last Visit" version of the C-SSRS. The study participants should be referred immediately to a Mental Healthcare Professional.

Investigators should contact the Medical Monitor, whenever possible, to discuss the withdrawal of a participant in advance.

Study participants **may** permanently discontinue rozanolixizumab **and** move into the Observation Period at the discretion of the Investigator, Medical Monitor, and Study Physician if any of the following events occur:

5. Study participant is noncompliant with the study procedures or medications in the opinion of the Investigator.
6. Study participant takes prohibited concomitant medications during the Treatment Period as defined in this protocol (Section 6.5.2).

Study participants who permanently discontinue IMP for reasons other than requiring rescue therapy will not be eligible for enrollment into the OLE study.

Study participants who withdraw from the study during the Treatment Period should complete the assessments outlined PEOT Visit and enter the Observation Period.

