3.2 General study level definitions

3.2.1 Analysis time points

All data will be analyzed based on the visits identified per the Schedule of Activities in protocol. Mapping to analysis visit windows is not applied, except for premature end of treatment (PEOT) visits (specified in [Section 3.2.3](#)).

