8.1 Handling of intercurrent events

The main intercurrent events (ICEs) of interest are:

- ICE1 – The use of rescue therapy prior to Day 43 (Visit 10)
- ICE2 – Permanent treatment discontinuation (or withdrawal from study) due to TEAEs

Two additional types of ICEs will be included to account for data affected by the COVID-19 pandemic as follows:

- ICE3 – Treatment discontinuation due to suspected/confirmed COVID-19 infection (“Confirmed COVID-19” or “Suspected COVID-19” as the relationship to COVID-19 in the COVID-19 Impact eCRF)
- ICE4 – Treatment discontinuation due to non-COVID-19 infection related issues (“General circumstances around COVID-19 pandemic without infection” or “other” as the relationship to COVID-19 in the COVID-19 Impact eCRF)

The number and percentage of study participants with each intercurrent event will be summarized by treatment group and RLZ total.

The strategies to handle ICEs are summarized as below:

Strategies	Description
Hypothetical & treatment policy strategy	
If study participants experience ICE1, data at and after the point of the ICE for the purpose of analysis will be treated as missing and imputed under proposed method per Section 4.2.1.
 
For participants experiencing ICE2-4, data in the Treatment Period from Baseline to Day 43 will be used regardless of whether any ICEs occurred, missing data will be imputed per Section 4.2.1.
 
For participants who permanently discontinue treatment or withdraw from the study during Treatment Period and who continue into the Observation Period, the observation phase data (collected bi-weekly) will be mapped to the nearest visit for primary analysis where treatment windows will be utilized for the mapping.

Treatment policy strategy	The data in the Treatment Period from Baseline to Day 43 will be used regardless of whether any intercurrent events occurred.
Composite strategy	The occurrence of any intercurrent events above will be handled by evaluating the corresponding study participants as treatment failures and imputed with a worst score (continuous) or non-responder (binary).
COVID-19 Hypothetical strategy	
If participant experience ICE1 and/or ICE2, then data at and after the point of the intercurrent event for the purpose of analysis will be treated as missing.
 
Additionally, participant experience ICE3, ICE4 or those that have visits in treatment period affected (e.g. visit performed by video call) will be completely removed from analysis.

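### Permanent non-rescue stoppers have no clearly scheduled Day 43 efficacy assessment, although the primary analysis uses their data to Day 43, and the SAP sections on visit mapping conflict.

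*Protocol*

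**What the plan says.** **Who leaves the treatment schedule.** Protocol 7.1.3 lists events after which participants must permanently stop and "move into the Observation Period if any of the following events occur". Section 7.1.2 says that a participant meeting a QTc criterion "will discontinue rozanolixizumab and move into the Observation Period". Section 7.2 allows the same move for noncompliance or prohibited medication, and says that those who withdraw during the Treatment Period "should complete the assessments outlined PEOT Visit and enter the Observation Period".

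**Text pointing the other way.** Section 7.1.2 also says: "The study participant should follow the visit schedule as described in the protocol and the eCRF be completed accordingly". Section 7.1.1 (liver) has the same sentence, while item 7 of 7.1.3 sends permanent liver discontinuers into the Observation Period.

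**Who stays on schedule.** Protocol 4.1 has rescued participants complete the remaining treatment visits and Visit 10 before they enter the Observation Period. Participants whose drug is stopped only temporarily (7.1.4) also keep to the visit schedule.

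**How the data are used.** SAP 8.1 sets scores at and after rescue (ICE1) to missing. For ICE2 to ICE4 (permanent discontinuation for adverse events, and COVID-19-related discontinuation), "data in the Treatment Period from Baseline to Day 43 will be used regardless of whether any ICEs occurred". For participants who stop or withdraw and enter the Observation Period, "the observation phase data (collected bi-weekly) will be mapped to the nearest visit for primary analysis", using treatment windows that are given no numbers. SAP 3.2.1 says: "Mapping to analysis visit windows is not applied, except for premature end of treatment (PEOT) visits". SAP 3.2.3 assigns PEOT data to the next scheduled visit after the last one completed.

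**The concern.** The Day 43 visit is secured for rescued participants, whose later scores the primary analysis discards. It is not clearly secured for permanent non-rescue stoppers, whose later scores the analysis wants. SAP 8.1 sees the difficulty and tries to fill the gap with observation visits. Those visits come every two weeks and treatment visits every week, so an observation visit can fall a week either side of Day 43. A programmer following 3.2.1 would not map them at all.

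Where no score reaches Visit 10, the mixed model handles it as missing at random (SAP 8.2.2), borrowing partly from participants still on drug. To that extent a treatment-policy quantity is estimated as a hypothetical one. If stoppers on active drug lose benefit, the drug effect is overstated.

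**Working it through.** **1. Spacing.** The Schedule of Activities puts Visits 10 to 14 on Days 43, 57, 71, 85 and 99. The gaps are 57 − 43 = 71 − 57 = 85 − 71 = 99 − 85 = 14 days, which agrees with the two-weekly spacing in SAP 8.1.

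**2. Inputs.**
- Stopping visits: the Schedule reviews drug discontinuation criteria at Visits 4, 5, 6, 8 and 9 (Days 8, 15, 22, 29, 36).
- Visit 10 window: 43 ± 2, so Days 41–45.
- MG-ADL is taken at all four observation visits. QMG, MG-C and MG Symptoms PRO are taken only at the second and fourth.
- Assumption A: PEOT is held at the stopping visit and observation visits follow at +14, +28, +42 and +56 days. SAP 3.2.2 supports this, because it ends the Treatment Period at Day 43 or PEOT and starts the Observation Period the next day. No section states the visit days.
- Assumption B: the undefined mapping window is the protocol's ±2 days.

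**3. Count under A and B.** Observation day = PEOT day + 14k, checked against Days 41–45.

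| PEOT day | MG-ADL days near 43 | MG-ADL in window | QMG, MG-C, PRO days (+28, +56) | In window |
|---|---|---|---|---|
| 8 | 36, 50 | no | 36, 64 | no |
| 15 | 43 | yes | 43, 71 | yes |
| 22 | 36, 50 | no | 50, 78 | no |
| 29 | 43 | yes | 57, 85 | no |
| 36 | 50 | no | 64, 92 | no |

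MG-ADL misses 3 of 5; the other scales miss 4 of 5.

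**4. Windows.** With PEOT on its nominal day, the observation visits' own windows (±3 or ±4) give nearest ranges of Days 32–40 and 47–53 (PEOT Day 8), 33–39 and 46–54 (Day 22), and 47–53 (Day 36). None reaches 41–45. If PEOT itself also moves by up to 2 days, a hit becomes possible on 3, 3 and 1 of the 5 PEOT days respectively. For PEOT on any day from 2 to 40 with exact 14-day steps, 27 of 39 days (69%) give no score in the window.

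**5. Other readings, MG-ADL.**
- Visits timed from the last dose, as Protocol 4.4 times the end-of-study visit, with that dose a week before the stopping visit: 2 of 5 miss.
- PEOT at the weekly visit after a last dose at Visits 4 to 9: 2 of 5.
- Observation visits fixed at Days 57–99: 5 of 5.
- Stoppers follow the visit schedule to Day 43: 0 of 5.
- Nearest treatment visit with no limit: 0 of 5, but Day 50 then serves as Visit 10. It is 50 − 43 = 7 days late and equally far from Day 57.
- Under SAP 3.2.3, a PEOT after a completed Visit 9 counts as Visit 10, which removes the Day 36 row from the misses.

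**6. Size.** Upper bound = s × m × d, where s is the active-arm permanent stopping rate, m the share of stoppers without a Day 43 score, and d the benefit lost. The documents give no stopping rate; 5–14% is assumed. Take d = 2.0, the top of the 1.5–2.0 range in SAP 2.4, and assume all of it is lost.
- m = 0.6: 0.05 × 0.6 × 2.0 = 0.06 to 0.14 × 0.6 × 2.0 = 0.168, about 0.17 points.
- m = 1: 0.05 × 2.0 = 0.10 to 0.14 × 2.0 = 0.28 points.

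**The case against.** The strongest reply is that the plan already covers much of this. SAP 8.1 anticipates stoppers and maps their later visits. Under assumption A, a Day 8 stopper gives off-drug scores on Days 22 and 36 and a Day 22 stopper on Day 36; these enter the model and inform that participant's Day 43 estimate. Sensitivity Analysis #2 (jump to reference) and Supplementary Analysis #1 (trimmed mean, worst score) test the missing-data assumption, and both are repeated for the continuous secondary endpoints. Protocol 9.3 expects many adverse-event stoppers to start rescue; their later scores are hypothetical by design whatever visits are held. Full loss of effect is also doubtful for late stoppers: Protocol 4.2 reports IgG back to baseline only by about Day 57 after single doses.

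All of this stands, and it limits the size. It does not remove the gap: sensitivity analyses probe an assumption but do not supply the missing score, and the mapping that 8.1 relies on is excluded by 3.2.1.

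A reader might infer more than the documents support:
- That every non-rescue stop loses Day 43. Temporary stops stay on schedule, and the liver and QTc sections can be read as keeping the visit.
- That three of five is a fact of the design. It rests on an unstated anchor and an assumed window.
- That the bias favours whichever arm has more stops. The mechanism needs a drug effect to lose, so it does not favour placebo if placebo has more stops.

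**Conclusion.** The point holds in limited form. For permanent non-rescue stoppers the protocol does not clearly schedule the Day 43 data that the primary estimand uses. The protocol passages on where these participants go, and the SAP passages on mapping, need reconciling. The misses are 3 of 5 stopping visits for MG-ADL and 4 of 5 for QMG, MG-C and MG Symptoms PRO under assumptions A and B; the range for MG-ADL across readings is 0 to 5. That spread is itself part of the problem, since sites and programmers cannot tell what to collect or map.

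The treatment-policy component becomes hypothetical only in part. The bounds of 0.06–0.17 and 0.10–0.28 points are ceilings. They rest on an assumed stopping rate, complete loss of a 2-point effect, no offsetting placebo stops, and no help from earlier off-drug scores. They should not be read as an expected bias. The remedy is still worth making because it is cheap and gives the analysis observed values.

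**What to change.** 1. In Protocol 7.1 and 7.2 and the Schedule of Activities, state that participants who permanently stop study drug but remain in the study, and have not withdrawn consent, have the Day 43 efficacy assessments. MG-ADL and the other patient-reported outcomes may be done virtually. Stopping rules and care do not change.
2. State the day from which observation visits are timed after a PEOT, and reconcile this with 4.4 and with the sentences on following the visit schedule in 7.1.1 and 7.1.2.
3. In SAP 3.2.1, list the observation-visit mapping of 8.1 as a second exception, and give explicit windows.

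For stoppers who attend, no stopping visit would then lack a Visit 10 score (0 of 5). The cost is a protocol amendment on assessment timing, SAP wording, and at most one added, partly virtual, assessment per early permanent stopper.

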7.1.4 Temporary IMP discontinuation

Study participant **must be** TEMPORARILY discontinued from the IMP if any of the following events occur:

1. The study participant develops an event of hypogammaglobulinemia with a serum total IgG of <1g/L irrespective of infection. When the IgG level reaches ≥2g/L, the study participant may be allowed to continue treatment with IMP (see Appendix 25; Section 10.25).

2. In the event of confirmed COVID-19 infection. IMP may be restarted if clinically appropriate when signs and symptoms have resolved.

Study participants ***may be TEMPORARILY discontinued from the IMP*** if the following events occur:

1. The study participant develops a non-serious persisting or recurrent infection with serum total IgG level between ≥ 1 and < 2 g/L. Upon resolution of infection and the IgG returning to level of ≥ 2 g/L, the study participant may be allowed to resume treatment with the IMP (see Appendix 25; Section 10.25).
2. In the event of suspected (eg, signs/symptoms such as fever, cough, shortness of breath) COVID-19 infection, or known exposure sufficient to necessitate testing or self-imposed quarantine, IMP may be restarted when clinically appropriate if:
 - a. COVID-19 test is negative, and signs and symptoms have resolved.
 - b. If test is not available, resolution of signs and symptoms and 14 days have passed since initial presentation of the clinical signs/symptoms.
 - c. If asymptomatic, 14 days have passed since known exposure.

The investigator should discuss with sponsor's study physician prior to re-initiating the IMP. As appropriate, virtual assessments could continue (eg, AE collection, PRO assessments).

If IMP treatment is resumed, continue the next dose as previously scheduled. No "make up" dose is permitted. The participant should subsequently follow the visit schedule as described in the protocol and the eCRF should be completed accordingly.

The study participant should follow the visit schedule as described in the protocol and the eCRF completed accordingly.

7.2 Participant Discontinuation/Withdrawal from the study

Study participants are free to withdraw from the study at any time, without prejudice to their continued care.

A study participant may also be withdrawn at any time at the discretion of the investigator for safety, behavioral, compliance, or administrative reasons.

If the study participant withdraws consent for disclosure of future information, the Sponsor may retain and continue to use any data collected before such a withdrawal of consent.

If a study participant withdraws from the study, he/she may request destruction of any samples taken and not tested, and the investigator must document this in the site study records.

See the Schedule of Activities (Section 1.3) for data to be collected at the time of study discontinuation and follow-up and for any further evaluations that need to be completed.

Study participants **must** be withdrawn from the study if any of the following events occur:

1. Study participant withdraws his or her consent.
2. The sponsor or a regulatory agency requests withdrawal of the study participant.
3. There is confirmation of a pregnancy during the study, as evidenced by a positive pregnancy test.

4. Study participant has active suicidal ideation as indicated by a positive response (Yes) to either Question 4 or Question 5 of the "Since Last Visit" version of the C-SSRS. The study participants should be referred immediately to a Mental Healthcare Professional.

Investigators should contact the Medical Monitor, whenever possible, to discuss the withdrawal of a participant in advance.

Study participants **may** permanently discontinue rozanolixizumab **and** move into the Observation Period at the discretion of the Investigator, Medical Monitor, and Study Physician if any of the following events occur:

5. Study participant is noncompliant with the study procedures or medications in the opinion of the Investigator.
6. Study participant takes prohibited concomitant medications during the Treatment Period as defined in this protocol (Section 6.5.2).

Study participants who permanently discontinue IMP for reasons other than requiring rescue therapy will not be eligible for enrollment into the OLE study.

Study participants who withdraw from the study during the Treatment Period should complete the assessments outlined PEOT Visit and enter the Observation Period.

